### **8.2.2.4 Modified Sartorius Score (mSS)**

The mSS is a summation of HS lesions based on a number of factors including anatomical region, number and type of lesions, and distance between relevant lesions measured as HS

---

clinical parameters [23]. The mSS has a minimum value of 0 and no upper limit and is calculated using data recorded for HS clinical parameters in the eCRF (Section 8.2.2.1) according to the algorithm in Appendix 17.3.

The mSS and the corresponding change from Day 1 will be assessed at each of the prespecified times when the HS clinical parameters are scheduled to be assessed during the study, as outlined in [Schedules of Assessments](#).

#### **8.2.2.5 Lesions**

Lesion counts are defined as the number of all abscesses, inflammatory nodules, non-inflammatory nodules, non-draining fistulas, draining fistulas, hypertrophic scars, and other lesions. Lesion counts will be recorded at each of the prespecified times when the HS clinical parameters are scheduled to be assessed during the study (as outlined in the [Schedules of Assessments](#)).

#### **8.2.2.6 Erythema Assessment**

For each anatomic region affected by HS, the investigator will assess the overall degree of erythema using a 4-point ordinal scale ranging between 0 and 3 (0 = no redness, 1 = faint but discernible pink coloration, 2 = moderate red coloration, 3 = very red or bright red coloration) (Appendix 17.4) through Week 44 (as outlined in the [Schedules of Assessments](#)) or early discontinuation visit and the 3-month Post-Treatment Follow-Up visit if the subject discontinues before Week 44.

The erythema assessment will be used to assess the worst and average degree of erythema for each affected anatomic region and overall.

#### **8.2.2.7 Patient's Assessment of Drainage**

The Patient's Assessment of Drainage (Appendix 17.5) will be assessed daily by subjects in an e-diary from Screening through the FUV at Week 44

The Patient's Assessment of Drainage will be used to assess the amount of drainage due to HS. Ratings affected by HS will range from 0 (no drainage) to 10 (drainage as bad as you can imagine).

#### **8.2.2.8 Analgesic Therapy**

Subjects will be required to report taking any analgesics. All use of analgesics and any dose adjustments will be recorded in the source documentation and in the eCRF. For further details refer to section 5.8.2.3.

#### **8.2.2.9 Patient's Global Assessment of Skin Pain (NRS)**

The Patient's Global Assessment of Skin Pain (NRS) (Appendix 17.6) will be assessed by subjects every day in an e-diary from Screening through the FUV at Week 44.

The NRS will be used to assess the worst and average skin pain due to HS. Ratings for these 2 items range from 0 (no skin pain) to 10 (skin pain as bad as you can imagine).

Subjects should be instructed to respond to the items based on a recall period of the "last 24 h". They should also document any analgesic therapy in the e-diary.

#### **8.2.2.10 Dermatology Life Quality Index (DLQI)**

The DLQI is an established and widely used patient-reported outcome instrument for assessing the impact on health-related quality of life due to dermatological conditions in clinical

---

studies. The DLQI will be assessed by subjects on Day 1 (Week 0) and during the study at prespecified times through Week 44 (as outlined in the [Schedules of Assessments](#)) or an early discontinuation visit and the 3-month Post-Treatment Follow-Up visit if the subject discontinues before Week 44.

A score is documented for each of the 10 DLQI items, ranging from 0 to 3 for each item. The total score is the sum of the responses to all 10 DLQI items, ranging from 0 to 30. A higher score corresponds to worse HRQL [20]. Guidelines with regard to the scoring of each question and the handling of incorrectly completed questionnaires are taken from the DLQI manual (<http://sites.cardiff.ac.uk/dermatology/quality-of-life/dermatology-quality-of-life-index-dlqi/dlqi-instructions-for-use-and-scoring/>). Details of the subject questionnaire and the evaluation of the total DLQI score are available in Appendix 17.7.

The DLQI score yields an efficacy endpoint.

To avoid biasing the subject's response, the subject should complete the questionnaire at the study site before study site personnel perform any other assessments and before any interaction with the study site personnel has occurred.

#### **8.2.2.11 Hospital Anxiety and Depression Scale (HADS)**

Subjects will complete the HADS questionnaire (Appendix 17.8) on Day 1 (Week 0) and during the study at prespecified times through Week 44 (as outlined in the [Schedules of Assessments](#)) or an early discontinuation visit and the 3-month Post-Treatment Follow-Up visit if the subject discontinues before Week 44. The HADS is a subject-rated scale designed to screen for anxiety and depressive states. It consists of 2 sub-scales: the D-scale measures depression and the A-scale measures anxiety. Each sub-scale contains 7 items and each item is rated from 0 (absent) to 3 (maximum severity). The score of each sub-scale ranges from 0 to 21.

To avoid biasing the subject's response, the subject should complete the questionnaire at the study site before study site personnel perform any other assessments and before any interaction with the study site personnel has occurred.

#### **8.2.2.12 36-Item Short Form Survey (SF-36v2)**

Subjects will complete the SF-36v2 questionnaire (Appendix 17.9) on Day 1 (Week 0) and during the study at prespecified times through Week 44 (as outlined in the [Schedules of Assessments](#)) or an early discontinuation visit and the 3-month Post-Treatment Follow-Up visit if the subject discontinues before Week 44. The SF-36v2 is a subject-reported generic measurement of health status that has proven useful in studies of both general and specific populations, comparing the relative burden of diseases and the health benefits produced by different treatments [24].

The SF-36v2 consists of 36 questions from the following 8 domains: vitality, physical functioning, bodily pain, general health perceptions, physical role functioning, emotional role functioning, social role functioning, and mental health.

Each domain is directly transformed into a scale from 0 to 100 on the assumption that each question carries equal weight. A lower score indicates a poorer health status; a higher score indicates a better health status (i.e., a score of 0 is equal to maximum disability and a score of 100 is equal to no disability). The 8 domains are summarized to form 2 distinct higher-ordered clusters (physical health and mental health).

To avoid biasing the subject's response, the subject should complete the questionnaire at the study site before study site personnel perform any other assessments and before any interaction with the study site personnel has occurred.

---

### **8.2.2.13 EuroQol-5L Dimensions Survey (EQ-5D-5L)**

Subjects will complete the EQ-5D-5L questionnaire (Appendix 17.10) on Day 1 (Week 0), and during the study at prespecified times through Week 44 (as outlined in the [Schedules of Assessments](#)) or an early discontinuation visit and the 3-month Post-Treatment Follow-Up visit if the subject discontinues before Week 44. The EQ-5D-5L is a standardized subject-reported measure of health status in terms of quality-of-life parameters, such as the subject's mobility, self-care, usual activities, pain and discomfort, and anxiety and depression. There are 5 categorical response choices for each of the 5 measures. In addition, subjects are asked to indicate "the state of your health today" on a visual analog scale of 0 to 100 (0 = worst imaginable health state, 100 = best imaginable health state) [25].

The EQ-5D-5L relates to the respondent's situation at the time the assessment is completed, therefore the subject does not need to recall their health status over the preceding days or weeks.

To avoid biasing the subject's response, the subject should complete the questionnaire at the study site before study site personnel perform any other assessments and before any interaction with the study site personnel has occurred.

### **8.2.2.14 Photographic Documentation of Affected Areas**

Subjects at prospectively selected sites may be asked to have photographs taken of the affected areas during the study. Subjects who consent will have photographs taken at prespecified times through Week 44 (as outlined in the [Schedules of Assessments](#)) or an early discontinuation visit and the 3-month Post-Treatment Follow-Up visit if the subject discontinues before Week 44. No formal analysis is foreseen.

## **8.3 Safety Variables**

### **8.3.1 Overview of Variables**

Safety will be assessed on the basis of the following variables:

- AEs
- Physical examination
- Vital signs
- ECG
- Laboratory safety parameters
- Pregnancy test
- Status of HIV, HBV, and HCV status at Screening
- ADA status

### **8.3.2 Methods of Assessment**

#### **8.3.2.1 Adverse Events**

The incidence, severity, and causality of AEs will be assessed at every visit from signature of the informed consent form at Screening to the subject's last evaluation according to the procedures described in Section 9.

---

### **8.3.2.2 Physical Examination**

A physical examination will be performed at Screening and during the study at prespecified times through Week 44 (as outlined in the [Schedules of Assessments](#)) or an early discontinuation visit and the 3-month Post-Treatment Follow-Up visit if the subject discontinues before Week 44. Physical examination findings that are related to the medical history will be recorded in the source documentation and in the eCRF.

A symptom-directed physical examination should be performed at all other visits, as warranted. An abnormality noted after starting treatment with IMP (Day 1) will be evaluated by the investigator for whether it constitutes an AE.

### **8.3.2.3 Vital Signs**

Vital sign determinations of systolic and diastolic blood pressure, pulse rate (counted for at least 30 seconds after 5 min in a sitting position), respiratory rate, and body temperature will be obtained at each visit to the study site. Blood pressure and pulse rate should be measured before blood draws are performed. Height and body weight will only be measured at Screening.

### **8.3.2.4 Electrocardiogram**

A resting 12-lead ECG will be performed at Screening and during the study at prespecified times through Week 44 (as outlined in the [Schedules of Assessments](#)).

Subjects who had a 12-lead ECG with normal findings performed during the 90 days before Screening will not be required to have a repeat ECG at Screening, provided all the relevant documentation specified in the protocol is available. If there are other findings that are clinically significant (CS), the investigator must contact the medical monitor at the CRO before enrolling the subject into the study.

Subjects will have a repeat ECG at Week 44 or at an early discontinuation visit and the 3-month Post-Treatment Follow-Up visit if the subject discontinues before Week 44.

Subjects can have a repeat ECG examination at any time during the study if considered warranted by the investigator.

An appropriately certified physician will interpret, sign, and date each ECG. Any clinical significant (CS) and non-clinical significant (NCS) findings will be recorded in the source documentation and in the eCRF. Each signed, original ECG will be reviewed by the clinical monitor for correctness (date, time, and clinically relevant abnormal findings, if applicable) and stored with the source documentation at the study site.

### **8.3.2.5 Laboratory Safety Parameters**

Laboratory safety parameters will be assessed at Screening and during the study at prespecified times through Week 44 (as outlined in the [Schedules of Assessments](#)) or an early discontinuation visit and the 3-month Post-Treatment Follow-Up visit if the subject discontinues before Week 44.

Blood samples should be obtained after the subjects have provided responses to questionnaires and after vital sign determinations have been completed, but before administration of IMP.

Analyses will be conducted by a certified central laboratory.

Instructions regarding the collection, processing, and shipping of samples for analysis of laboratory safety parameters will be available in the laboratory manual provided by the responsible CRO. Instructions for urine pregnancy testing are also provided in the laboratory manual.

---

The following parameters will be assessed using standard validated methods:

Clinical chemistry: serum creatinine, urea, alanine transaminase, aspartate transaminase, gamma-glutamyltransferase, total bilirubin, lactate dehydrogenase, alkaline phosphatase, sodium, potassium, calcium, albumin

Hematology: red blood cells (erythrocytes), platelets, hemoglobin, white blood cells (including differential blood count)

Coagulation: partial thromboplastin time, international normalized rate

All abnormal laboratory values will require a comment in the eCRF according to the following classification:

- Not CS
- CS
- Error (e.g., laboratory error, improper sample preparation, hemolysis, or delayed transit to laboratory)

At Screening, any laboratory value that deviates from the reference range and is considered by the investigator to be CS, or considered as a result of a disease noted in the medical history, must be documented on the medical history page of the eCRF. Any deviation outside of the reference range considered by the investigator as CS at any later visit must be documented in the eCRF as an AE if not previously documented as an ongoing medical condition or as an ongoing AE. Follow-up laboratory investigations due to an AE will be performed at a local laboratory at the discretion of the investigator.

### **8.3.2.6 Pregnancy Testing**

Pregnancy testing will be conducted in all women of childbearing potential.

A serum pregnancy test will be performed at Screening, at Week 44 or an early discontinuation visit and the 3-month Post-Treatment Follow-Up visit if the subject discontinues before Week 44.

An urine pregnancy test will be performed at Weeks 0 (Day 1) and 16.

For France: an urine pregnancy test will be performed in addition at Weeks 4, 8, 12, 20, 24, 28, 32, 36, 40).

If any pregnancy test is positive, the subject will not be eligible for participation or continuation in the study.

Lactating women will not be eligible for participation or continuation in the study.

### **8.3.2.7 Human Immunodeficiency Virus (HIV) and Hepatitis Virus (HBV or HCV) Testing**

Tests for HIV-1 or 2 and HBV or HCV will be conducted at Screening.

Analyses for HIV-1 or 2 antibodies will be conducted by the central laboratory. Subjects will not be eligible for participation in the study if they test positive for HIV infection.

Analyses for the presence of HBV surface antigen (HBsAg) will be conducted by a central laboratory. Subjects will not be eligible for participation in the study if they test positive for HBsAg. Subjects who test negative for HBsAg will be tested for the presence of HBV surface antibody (HBsAb) and IgM-antibody against hepatitis B core antigen (IgM anti HBc). If test results are positive for HBsAb or IgM anti HBc, then an HBV DNA PCR test will be conducted. If "target is not detected" for the DNA PCR, the patient is eligible to enter the study. If test results are negative for HBsAB and IgM anti HBcA, patient is eligible to enter the study.

---

Analyses for the presence of anti-hepatitis C antibodies in serum will be conducted by a central laboratory using a standard chemiluminescence assay.

#### **8.3.2.8 Antidrug Antibodies**

ADAs will be assessed on Day 1 (before first administration of IMP) and during the study at prespecified times through Week 44 (as outlined in the [Schedules of Assessments](#)). A portion of the samples will be collected for possible future analysis; this is not applicable for patients in Denmark.

In addition, serum samples for future research taken at Week 2 (Day 15) will be used for ADA measurement.

ADAs will be measured in serum samples at a specialized laboratory using a validated homogeneous electrochemiluminescence-based bridging enzyme-linked immunosorbent assay for initial detection as well as an additional confirmatory assay in case of positive findings detected in the initial test. Samples that are confirmed as ADA-positive will be quasi-quantified by titration.

### **8.4 Pharmacokinetics and Pharmacodynamics**

#### **8.4.1 Overview of Variables**

PK will be assessed on the basis of IFX-1 concentrations.

PD will be assessed on the basis of the following variables:

- Complement factors C3a and C5a
- CH50
- CRP

#### **8.4.2 Methods of Assessment**

##### **8.4.2.1 Pharmacokinetic Variables**

Concentrations of IFX-1 in citrate plasma will be analyzed on Day 4 and during the study at prespecified times through Week 44 (as outlined in the [Schedules of Assessments](#)) or an early discontinuation visit and the 3-month Post-Treatment Follow-Up visit if the subject discontinues before Week 44.

In the PK substudy, the PK of IFX-1 will be assessed in approximately 10 subjects from each Cohort at Weeks 2 and 16 of the Main Period. At these times, blood samples will be obtained for the analysis of IFX-1 in citrate plasma before IMP infusion (0 h) and at after end of IMP administration (+10 min), and at 2 h ( $\pm 10$  min), 6 h ( $\pm 10$  min), 24 h ( $\pm 2$  h), and 48 h ( $\pm 2$  h) after start of IMP administration, in all cases using a separate infusion line.

IFX-1 will be analyzed by a specialized laboratory with an ELISA test system.

##### **8.4.2.2 Pharmacodynamic Variables**

The PD variables will be assessed on Day 1 and during the study at prespecified times through Week 44 (as outlined in the [Schedules of Assessments](#)) or an early discontinuation visit and the 3-month Post-Treatment Follow-Up visit if the subject discontinues before Week 44.

Complement factor C3a will be analyzed in plasma samples by a specialized laboratory with an ELISA test system.

---

Complement factor C5a will be analyzed in plasma samples by the specialized laboratory at InflaRx with an ELISA test system.

Total complement hemolytic activity CH50 will be analyzed in serum samples by the central laboratory with a liposome immunoassay.

CRP will be analyzed in serum samples by the central laboratory with a standard assay.

### **8.4.2.3 Serum and Plasma Biomarker Variables**

Samples to assess serum and plasma biomarkers will be taken on Day 1 and during the study at prespecified times through Week 44 (as outlined in the [Schedules of Assessments](#)) or an early discontinuation visit and the 3-month Post-Treatment Follow-Up visit if the subject discontinues before Week 44.

The collection of serum and plasma biomarker samples are not applicable for Denmark.

Samples may be analyzed for plasma and serum proteins, peptides, and non-protein soluble factors such as lipids that could help predict disease behavior or help determine more severe disease phenotypes. The samples may be analyzed as part of a multi-study assessment of factors involved in the response to IFX-1. The samples may also be used for the development of diagnostic tests related to IFX-1. The results of any such analyses may be reported separately.

Serum samples taken at Week 2 (Day 15) will be used for ADA measurement (Section [8.3.2.8](#)).

## **9 ADVERSE EVENTS**

### **9.1 Adverse Events**

#### **9.1.1 Definition of Adverse Events**

An AE is any untoward medical occurrence in a subject administered an IMP; an AE does not necessarily have to have a causal relationship with this treatment.

AEs encompass any unfavorable and unintended sign (including an abnormal laboratory finding), symptom, or disease that arises or worsens after the inclusion of the subject into the study.

AEs may include:

- The significant worsening of the disease or symptoms of the disease under investigation following administration of an IMP
- Illnesses that coincide with an onset after administration of an IMP
- Exacerbation (i.e., increase in frequency or severity) of a pre-existing condition. Chronic illnesses present prior to study entry, other than the indication being investigated, should be recorded in the medical history page of the eCRF and only be reported as AEs if there is an increase in the frequency or severity of the condition during the study
- For laboratory safety parameters, any absolute values outside of the reference range or changes after initial administration of the IMP that are considered by the investigator as CS must be recorded in the eCRF as AEs if not previously documented as ongoing medical conditions or as ongoing AEs. Examples of laboratory abnormalities that should be considered as AEs include those that result in discontinuation of treatment with the

---

IMP, withholding treatment with the IMP pending some investigational outcome, reduction of IMP dose, or additional concomitant treatment

- Laboratory abnormalities do not need to be listed as separate AEs if they are considered to be part of a clinical syndrome that is being reported as an AE

Laboratory findings do not need to be reported as AEs in the following cases:

- Laboratory parameters already beyond the reference range at baseline
- Abnormal laboratory parameters caused by mechanical or physical influences on the blood sample (e.g., hemolysis) and flagged as such by the laboratory in the laboratory report
- Abnormal parameters that are obviously biologically implausible (e.g., values that are incompatible with life)
- An abnormal laboratory value that cannot be confirmed after repeated analysis, preferably in the same laboratory (i.e., the previous result could be marked as not valid and should not necessarily be reported as an AE)

In addition, at the investigator's discretion, any changes or trends over time in laboratory parameters can be recorded in the eCRF as AEs, if such changes or trends are considered to be clinically relevant, even if the absolute values are within the reference range.

AEs do not include:

- Medical or surgical procedures; the condition that leads to the procedure is an AE
- Untoward medical findings that occur before initial administration of the IMP if they occur in the scope of investigations that are performed for assessing inclusion and exclusion criteria (e.g., results of laboratory tests conducted at Screening)
- Situations where an untoward medical occurrence has not occurred, e.g., planned hospitalization due to a pre-existing condition that has not worsened, hospitalization that occurs for a procedure not associated with an AE (e.g., elective surgery or social admission), or hospitalization for a diagnostic procedure that takes less than 24 h
- Overdose of an IMP or any concomitant therapy that does not result in any adverse signs or symptoms. Details of the dosing (volume, location of infusion, and infusion rate) of the IMP will be recorded in the eCRF

At each visit to the study site, the investigator will determine whether any AEs have occurred. If known, the medical diagnosis of an AE should be recorded in preference to the listing of individual signs and symptoms.

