
11. One of the following abnormal laboratory findings:
 
 
a. WBC < 2500/mm^3
 
b. Neutrophil count < 1000/mm^3
 
c. Serum creatinine > 3 × UNL
 
d. Total bilirubin > 3 × UNL
 
e. Alanine aminotransferase > 5 × UNL
 
f. Aspartate aminotransferase > 5 × UNL
 
g. Positive Screening test for HIV-1 or 2, or hepatitis B or C virus
 
 
For Canada only: One of the following abnormal laboratory findings:
 
 
a. WBC < 2500/mm^3
 
b. Neutrophil count < 1000/mm^3
 
c. Serum creatinine > 3 × UNL
 
d. Total bilirubin > 1.5 × UNL
 
e. Alanine aminotransferase > 2.5 × UNL
 
f. Aspartate aminotransferase > 2.5 × UNL
 
g. Positive Screening test for HIV-1 or 2, or hepatitis B or C virus
 
	Safety concern	X	

12. Chronic and/or recurring systemic infections, history of invasive infections with atypical pathogens (i.e., which normally do not cause invasive infection, such as listeriosis), or known primary immunodeficiency
	Safety concern	X	

13. Subject is judged to be in poor general health, as determined by the investigator based upon medical history, physical examination, laboratory safety and, a 12-lead ECG
	Safety concern		X

14. Female subjects of childbearing potential unwilling or unable to use a highly effective method of contraception (pearl index < 1%) such as complete sexual abstinence, combined oral contraceptive, vaginal hormone ring, transdermal contraceptive patch, contraceptive implant, or depot contraceptive injection in combination with a second method of contraception such as condom, cervical cap, or diaphragm with spermicide during the study and for at least 1 month after last administration of IMP. For France only: the methods of contraception are applicable during the study and for at least 3 months after last administration of IMP.	Safety concern	X	X
15. History of drug or alcohol abuse during the 24 weeks before Screening	Safety concern	X	
16. Pregnancy, as verified by a positive pregnancy test, or nursing woman	Safety concern	X	X
17. Evidence or suspicion that the subject might not comply with the requirements of the study protocol	Safety concern	X	

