### 10.4.2 Safety Endpoints

The number and percentage of subjects who had a TEAE as well as the number of TEAEs will be assessed for all TEAEs and SAEs.

Furthermore, the number and percentage of subjects who have a TEAE as well as the number of TEAEs will be assessed for all causally related TEAEs, related SAEs, AESIs, TEAEs leading to study discontinuation, related TEAEs leading to study discontinuation, TEAEs leading to IMP discontinuation, and related TEAEs leading to IMP discontinuation.

For the analysis of severity and causal relationship of AEs, the worst severity and the strongest relationship per subject and class of AE will be considered.

Laboratory safety parameters, especially the change in inflammatory markers and differential blood cell counts, will be assessed by time point and changes in routine laboratory parameters from baseline will be determined. Shifts in safety laboratory parameters outside of normal ranges compared with baseline will be investigated.

Immunogenicity will be assessed by determining the number and percentage of subjects with detection of ADAs (before and after administration of IMP).

Other safety endpoints will be exploratory, as defined in detail in the statistical analysis plan.

Non-treatment-emergent AEs will be listed.

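### The AE exemption for laboratory values already abnormal at baseline has no worsening condition and conflicts with the protocol's own worsening and clinical-significance rules

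*Combined protocol and SAP*

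**What the plan says.** Four parts of the protocol bear on this point.

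- **Exemption (9.1.1).** The list opens with "Laboratory findings do not need to be reported as AEs in the following cases", and its first case is "Laboratory parameters already beyond the reference range at baseline". Nothing is said about later worsening.
- **Duty to record (9.1.1 and 8.3.2.5).** The general AE definition names abnormal laboratory findings and covers any sign, "symptom, or disease that arises or worsens after the inclusion of the subject into the study". Another bullet lists "Exacerbation (i.e., increase in frequency or severity) of a pre-existing condition" among possible AEs. For laboratory parameters, "changes after initial administration of the IMP that are considered by the investigator as CS must be recorded in the eCRF as AEs", except where already documented as ongoing conditions or AEs. Section 8.3.2.5 repeats this for later visits: a CS deviation "must be documented in the eCRF as an AE if not previously documented as an ongoing medical condition or as an ongoing AE". It also sends Screening deviations that are CS, or that result from a disease in the history, to the medical history page.
- **Entry limits (4.2, criterion 11).** Exclusion starts at "Alanine aminotransferase > 5 × UNL", with the same limit for AST. Bilirubin and creatinine are each limited at 3 x UNL, neutrophils at 1000/mm3 and WBC at 2500/mm3. Canada has tighter liver limits: 2.5 x UNL for ALT and AST, and 1.5 x UNL for bilirubin.
- **Use of the data (10.4.2 and 10.5.2).** Counts of TEAEs and SAEs are the named safety endpoints. Laboratory values are also summarised separately by visit, and "Shifts in safety laboratory parameters outside of normal ranges compared with baseline will be investigated".

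**The concern.** The other three cases in the exemption list are a sample artefact, a biologically implausible value and a value that repeat analysis does not confirm. None of these is a real event. The baseline case is different, because it can cover a confirmed change on treatment. Section 9.1.1 makes increased frequency or severity the test for reporting a pre-existing chronic illness, but the laboratory bullet has no such test.

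What is at stake is AE-level information. Section 9.1.2 attaches severity, causality, seriousness and follow-up to outcome to AEs, not to laboratory values as such. A worsening that is not recorded as an AE misses those steps and is absent from the TEAE counts. With approximately 50 planned sites, the counts would partly depend on which of two conflicting sentences each site follows.

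Section 1.2 lists acute hepatic failure and hepatocellular injury among AEs reported as at least possibly related to IFX-1. Those events arose in subjects with early septic organ dysfunction. The same section reports no possibly related AEs in the 12 treated subjects of the earlier hidradenitis study. This is a reason for tidy liver reporting, not evidence of a liver signal in this population.

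**Working it through.** The plan states no figure to reproduce, so the check sets the rules side by side.

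**Step 1: can a subject fall under the exemption?** Section 10.6 defines baseline as the last measurement before first IMP. The Main Period schedule and Section 7.2 show no safety laboratory sample on Day 1, so baseline is normally the Screening value. Criterion 11 then admits these out-of-range values:

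| Parameter | Admitted | Admitted, Canada |
|---|---|---|
| ALT, AST | up to 5 x UNL | up to 2.5 x UNL |
| Total bilirubin | up to 3 x UNL | up to 1.5 x UNL |
| Creatinine | up to 3 x UNL | up to 3 x UNL |
| Neutrophils | 1000/mm3 or more | 1000/mm3 or more |
| WBC | 2500/mm3 or more | 2500/mm3 or more |

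For the parameters limited by UNL, anything above 1 x UNL is out of range by definition. For the two cell counts, I assume that the laboratory's lower limits lie above these cut-offs; the documents do not give them. So the answer is yes.

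**Step 2: what do the rules require when such a value worsens?**

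| Situation | Baseline exemption | CS rule (9.1.1, 8.3.2.5) | Result |
|---|---|---|---|
| Screening value out of range, not CS and not in medical history; later change judged CS | need not report | must report | direct conflict |
| Screening value entered in medical history as an ongoing condition; later change judged CS | need not report | lapses by its own exception | only the general definition and the exacerbation bullet point to an AE |
| Screening value in range; later deviation judged CS | does not apply | must report | clear |
| Worsening leads to stopping, withholding or reducing IMP, or to added treatment | need not report | 9.1.1 says such abnormalities should be considered AEs | conflict |

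Section 9.1.1 also allows clinically relevant changes or trends to be recorded, but at the investigator's discretion. That permits a record without requiring one. No sentence ranks the rules.

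**Step 3: what is lost and what is kept?**

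- Lost if a site follows the exemption literally: the TEAE record and its severity, causality and follow-up assessment.
- Kept: a CS or not-CS comment on every abnormal value in the eCRF (8.3.2.5), individual listings (10.1), by-visit summaries of absolute values and changes with minimum and maximum (10.5.2), and laboratory results supplied to the DMC (13.3).

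**Step 4: size.** The documents do not give the share of subjects with an out-of-range baseline value, and the exemption works parameter by parameter, so the number affected cannot be computed. The effect of a single omission can be. With 35 subjects per cohort, one subject is 1/35 = 0.0286, or 2.9 percentage points of the cohort TEAE rate, provided that the subject has no other TEAE. If the subject has another, only the event count changes.

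**The case against.** The best reply is that the protocol already requires the right thing. The exemption bullet does not say that worsening values are exempt; it is silent. The general definition covers worsening, and CS changes after first dosing must be recorded. A reader might take a rise in ALT from 1.5 to 15 x UNL as plainly exempt. The documents do not support that: if the Screening value was judged not CS and was not in the medical history, the CS rule would still require an AE record once the rise was judged CS. The exemption also concerns laboratory findings, not diagnoses. Sections 9.1.1 and 9.1.2 ask for the diagnosis where known, and the SAE criteria in 9.2.1 have no baseline exemption. Clinical liver injury would therefore be reportable whatever the baseline value.

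Much of this stands. It shows that the protocol contradicts itself, not that it sets out to exclude worsening. It does not remove the problem, because no text gives the CS rule precedence, and for subjects whose abnormality is in the medical history the CS rule switches itself off.

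It might also be said that the shift analysis cannot show worsening from high to higher. Section 10.4.2 does not define the shift categories, so this is a possibility to guard against and not an established defect.

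**Conclusion.** The point holds as an unresolved contradiction within 9.1.1, carried into 8.3.2.5 by the ongoing-condition exception. Sites could inconsistently leave on-treatment worsening out of the TEAE counts and out of AE-level assessment, for subjects whom the entry criteria admit. This rests on some sites applying the exemption literally; it does not assume that all would.

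Two stronger readings should be resisted. One is that toxicity would be hidden from safety review. It would not, because the values reach the summaries, the listings and the DMC. The other is that the dose-safety comparison would be biased toward no difference. The exemption applies to placebo as well. If the omitted fraction were similar across cohorts, risk ratios would be unchanged and only absolute differences would shrink. The documents give no basis for estimating that fraction. A wording correction is warranted because it is cheap and concerns a named safety endpoint.

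**What to change.** 1. In 9.1.1, limit the baseline exemption to parameters that were out of range at baseline and have not since worsened to a degree that the investigator considers clinically significant.
2. In the CS bullet of 9.1.1 and in 8.3.2.5, qualify the exception for conditions or AEs already documented as ongoing, so that it does not apply when the value has become clinically significantly worse than what was documented.
3. Optionally, specify shift tables that show worsening within the abnormal range, so that high-to-higher and low-to-lower changes are visible.

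The first two changes use the protocol's existing investigator judgement of clinical significance and introduce no new threshold. No extra sampling is needed. The cost is a short amendment to two sections, one table layout if the third item is adopted, and a few more AE records.
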